### **Aim 3: Assess preliminary outcomes of the peer mentoring program.**

*Hypothesis 3 (Phase 2):* Participants in the mentor group will demonstrate improvement in self-management skills, transition readiness, and anxiety.

*Hypothesis 4 (Phase 3):* Participants in the self-management + peer mentor intervention will demonstrate greater improvement in transition readiness than participants in the usual care group.

*Hypothesis 5 (Phase 3):* Participants in the self-management + peer mentor intervention will participate in survivorship and preventive healthcare at greater rate than participants in the usual care group.

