### **3.3 Sample Size Justification**

Phase 1: Total sample size is 24-28, including 10 AYA survivors, 10 parents of AYA survivors, and 4-8 physicians who work with AYA survivors. Qualitative data will be analyzed on a continuing basis. Pooling data across participants, we expect 24-28 interviews will be adequate to achieve data saturation (that is, no new themes emerge from additional participants).

Phase 2: 40 AYA survivors and 20 peer mentors will be recruited for the pilot trial to evaluate feasibility (primary objective) and preliminary outcomes (secondary objective). As this is a feasibility study, we recognize we are underpowered to detect small or medium effects. Published data suggest 5-9% of survivors are African American or Hispanic; data from the NJSCR show greater diversity, with 11.6% of patients diagnosed with cancer at age 10-19 during the period of 2008-2012 reporting as African American, 19% reporting as Hispanic, and 5.7% as Asian American/Pacific Islander. We will oversample these groups.

Phase 3A: Up to 20 AYA survivors will be recruited for usability testing of the online intervention. Given the preliminary work conducted in Phase 2, we expect 12-20 sessions will achieve data saturation (i.e., no new issues emerge according to pre-specified stopping criteria). Usability testing is designed to be iterative in that changes can be made to the site after a small number of participants. Therefore, participants who agree may be asked to complete multiple usability sessions over the course of a few months to provide additional feedback on changes or new features added. Thus we expect about 12 to 20 participants will be needed to achieve data saturation.

Phase 3B: Total sample size is 50 AYA survivors. We chose the sample size and decision rules so that the probability of declaring feasibility would be approximately 5% under unacceptable rates of acceptance/completion and exceed 95% under acceptable rates. If true acceptance and completion rates were 41% and 70%, respectively, which we consider too low to move to an efficacy trial, then the probability of declaring feasibility would be 5%.

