#### **4.2 Dependent Variables or Outcome Measures**

Phase 1: The primary outcome measure is qualitative interview data. Interviews will be transcribed for analysis (see Data Handling and Statistical Analysis section for details). Participants will also be asked to complete the questionnaires selected for Phase 2 and provide feedback to the study staff regarding how well the questionnaires capture self-management of survivorship care.

Phase 2: The following standardize measures will be administered at baseline and immediately post-intervention (~6 weeks), except where noted:

*Transition readiness.* The Readiness for Transition Questionnaire – Survivor Version (RTQ) is a 22-item scale evaluating transition readiness for cancer survivors. Respondents are asked to rate the degree to which they are responsible for various aspects of their health care, such as knowing their survivorship care plan, scheduling visits, and filling prescriptions. They are separately asked to rate the degree to which their parents are responsible for managing the same aspects of their care. Two questions ask about the survivors' overall perception of their readiness to transfer to an adult-approach to health care. The RTQ has demonstrated adequate reliability.

The Transition Readiness Inventory (TRI), developed using the SMART framework, is a comprehensive measure of multiple components of transition readiness. While the RTQ focuses on responsibility for behaviors, the TRI focuses on behaviors *and knowledge, attitudes, and beliefs*. Specifically, the TRI yields a total score and provides scales for the following targets of our intervention: knowledge, self-management skills, self-efficacy for managing care, goals/motivation, and communication with family and providers around survivorship care. The TRI has shown adequate reliability and content validity, and evidence of predictive validity of engagement in adult healthcare. We will utilize the total TRI score.

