Participants will complete surveys online or via paper (depending on participants' choice). Paper surveys will be identified using only a subject number and will be entered into the database by study staff and kept in a locked filing cabinet accessible only by authorized study staff. We will keep a separate electronic key linking codes and subject names on the PI's department drive. This key will be destroyed at the end of the study. De-identified data will be kept indefinitely. Audio files of video/phone calls between peer mentors and mentees will be recorded using the peer mentor's handheld audio recorder. The peer mentor will then use Rutgers Large File Transfer Service (LiFT) to securely upload the files for the study team to review. This service allows both internal and external users to upload files securely with their email and password. The peer mentors will be instructed to destroy the files after they have successfully uploaded files to Rutgers LiFT for study team to review. Peer mentors will receive training on how to securely transfer the files and delete the files from their devices during the mandatory in-person peer mentor training. The study team will download the files via the secure LiFT service and store them on the Rutgers secure shared drive accessed via a password-protected computer. For participant exit interviews, study staff will record the interview, transfer to the secure shared drive (access limited to pertinent research team members). Recordings will be transcribed as soon as possible, removing any identifying information from the written document. Recordings will be destroyed upon completion of the study procedures.

**Data Analysis:** We will examine feasibility through study enrollment rates, retention rates, reasons for study drop out, adherence to the intervention, and patient and mentor satisfaction with the program. Descriptive analyses (frequencies, means) will be used to evaluate our hypotheses regarding expected enrollment (>50%), retention (>75%), and completion of intervention sessions (>75%). We based these predictions using the literature describing barriers to recruiting AYA participants and the team's collective experience in intervention development and implementation.

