To assess the preliminary outcomes of the peer mentor self-management program, we will evaluate whether participants in the program demonstrate improvement in transition readiness and the impact of cancer, and reductions in symptoms of depression and anxiety. We will also explore adherence outcomes. We will compare scores on outcome measures at the end of 6-week assessment using dependent/paired t-tests. Since the primary purpose of this project is to evaluate feasibility, we recognize that we do not have adequate power to detect small to medium statistical effects. Exit interviews will be reviewed to identify strengths of the intervention, weaknesses of the intervention, and ideas to improve the intervention.

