### Phase 3B:

**Data Management:** The same procedures used in Phase 2 will be used in Phase 3B, with the exception that TigerConnect (previously called TigerText) will be used for secure messaging as well as secure videoconferencing (instead of doxy.me). Additionally, TigerConnect now allows for secure file transfer so that peer mentors can securely transfer audio recordings to the study team either via Rutgers LiFT or TigerConnect. For participants who consent to be contacted for future studies, the study team will store their contact information separately from research records on the PI's secure One Drive, with access granted only to the PI, study coordinator, and limited authorized research staff. We will store this information for up to 10 years from date of consent.

We will utilize HIPAA compliant Qualtrics survey tool to request the name and contact information of the physician they have seen in the past 12 months to understand their health care utilization during the study period and to obtain their electronic signature on the Release of Medical Record form. Any paper copies will be kept in a locked filing cabinet in the PI's office.

**Data Analysis:** We will examine feasibility through study enrollment rates, retention rates, usability/engagement with online modules and peer mentor, barriers to engagement, and reasons for study drop out. Descriptive analyses (frequencies, means, confidence intervals) will be used to evaluate hypotheses regarding enrollment ( $>50\%$ ), retention ( $>80\%$  complete all surveys), and intervention completion ( $>75\%$  modules/mentor calls). Multilevel modeling (MLM) will be used to examine differences between the intervention and usual care groups over time on transition readiness (RTQ Adolescent Responsibility and TRI total scores). Our primary analysis will consider both time and treatment to be categorical with an interaction between the two. The interaction will be assessed to determine whether change in transition readiness differs between the two groups. The MLM approach assumes any missing observations are missing at random but includes all observed data. Exploratory analyses of additional outcomes (e.g., self-efficacy, adherence to medical appointments and screenings, and health behaviors) will use the identity link or the logit link as appropriate for continuous or binary outcomes.

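### The Phase 2 paired t-tests analyse only survivors with both scores, while Hypothesis 3 concerns all programme participants; the direction and size of any resulting bias are unknown

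*Combined protocol and SAP*

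**What the plan says.** Phase 2 is a single-arm pilot. Section 3.3 sets its size and priorities: "40 AYA survivors and 20 peer mentors will be recruited for the pilot trial to evaluate feasibility (primary objective) and preliminary outcomes (secondary objective". Section 4.2 says the standardised measures are "administered at baseline and immediately post-intervention (~6 weeks), except where noted", so an outcome has at most two scores per survivor.

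Hypothesis 3 (Section 1.1, Aim 3) reads: "Participants in the mentor group will demonstrate improvement in self-management skills, transition readiness, and anxiety". Section 5, Phase 2, uses a similar target: "we will evaluate whether participants in the program demonstrate improvement in transition readiness and the impact of cancer". Neither is limited to those who finish. The analysis is then given in one sentence: "We will compare scores on outcome measures at the end of 6-week assessment using dependent/paired t-tests".

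The Phase 2 data analysis text in Section 5 expects retention above 75%. Hypothesis 1 in Section 1.1, which is not tied to a phase, expects more than 80%. Reasons for drop-out are to be examined, but the Phase 2 text names no analysis set, no method for missing outcome scores and no sensitivity analysis. Phase 3B does address the matter: "The MLM approach assumes any missing observations are missing at random but includes all observed data".

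**The concern.** A paired t-test works on within-person differences. A survivor without a 6-week score has no difference, so that person's baseline is discarded too. The test answers whether those who were reassessed improved. The hypothesis asks whether participants improved.

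The two questions have the same answer if loss is unrelated to change. They can differ in two ways. Loss may depend on the baseline score, which is observed. Or it may depend on the 6-week outcome, which is not. With no comparison arm, there is no control change against which selective loss could partly cancel, so any effect goes straight into the mean change. At stake is whether a gain among completers is reported as the gain of the programme's participants.

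**Working it through.** **Plan's own figure.** The documents give no power, effect size or bias figure for the Phase 2 t-tests, so there is nothing to reproduce first.

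**Inputs from the documents.** N = 40 (Section 3.3); retention r = 0.75 (Section 5, Phase 2) or 0.80 (Hypothesis 1); SD 0.83 for the RTQ Adolescent Responsibility score at baseline (Section 3.3, given there for Phase 3B).

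**Assumed inputs.** f, the mean gain of leavers as a fraction of the completers' gain; a baseline to 6-week correlation of 0.6; a completer gain of 0.30. The documents give none of these.

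**Step 1: number excluded.** 40 × (1 − 0.75) = 10; 40 × (1 − 0.80) = 8. The targets are floors, so these are the largest losses consistent with them.

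**Step 2: completer mean against the 40-person mean.** If completers gain g, the mean over all 40 is g × [r + (1 − r)f]. The relative excess of the completer mean is therefore 1/[r + (1 − r)f] − 1.

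| Assumed gain of leavers | r = 0.75 | r = 0.80 |
|---|---|---|
| 1.5 times completers' (f = 1.5) | −11.1% | −9.1% |
| Same (f = 1) | 0% | 0% |
| Half (f = 0.5) | 14.3% | 11.1% |
| None (f = 0) | 33.3% | 25.0% |
| Worsen by half (f = −0.5) | 60.0% | 42.9% |

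For example, at r = 0.75 and f = 0.5: 1/(0.75 + 0.125) − 1 = 0.143. At 90% retention the excess is 11.1% for f = 0 and 5.3% for f = 0.5.

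**Step 3: does a model using all observed data help when loss follows the outcome?** Take a completer gain of 0.30, a leaver gain of zero and loss unrelated to baseline. The true 40-person mean is 0.75 × 0.30 = 0.225 or 0.80 × 0.30 = 0.24. In simulation (20,000 runs) the paired mean was 0.30 and the likelihood estimate that keeps every baseline was also 0.30. The model removes none of the excess, because it fills in leavers from completers with similar baselines.

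**Step 4: does it help when loss follows the observed baseline?** Suppose the true gain is 0.30 for everyone apart from regression to the mean. With equal variances and correlation 0.6, expected change given baseline is 0.30 − (1 − 0.6) × (baseline − mean). If completers' mean baseline differs from the overall mean by d, the paired mean is about 0.30 − 0.4d. Fairly strong dependence of loss on baseline gives |d| of about 0.21 (32 retained) to 0.26 (30 retained):
- low scorers leave: 0.30 − 0.4 × 0.21 = 0.22, and 0.30 − 0.4 × 0.26 = 0.20;
- high scorers leave: 0.38 and 0.40.

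The same simulation gave 0.20-0.22 and 0.38-0.40 for the paired mean and 0.30 for the likelihood model. Here the model does correct the bias, whichever its direction.

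**Step 5: scale.** The SD of change is 0.83 × √(2 × 0.4) = 0.742, so the standard error of the paired mean is 0.742/√30 = 0.136 or 0.742/√32 = 0.131. The zero-gain bias in Step 3 is 0.06 to 0.075, about half a standard error.

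**The case against.** The strongest objection is that little hangs on this result. Feasibility is the primary objective of Phase 2 and outcomes are secondary. Section 5 concedes that power is inadequate for small to medium effects. No go/no-go rule uses the Phase 2 mean change: Phase 3 follows from participant feedback, the Phase 3B sample size rests on feasibility rules and external survey data, and efficacy is carried to a randomised comparison. All of that stands and sets the priority. It does not remove the mismatch, because a caveat about low power warns of missed effects, not of a selected sample.

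A second objection is that leaving the study is not the same as failing to engage. The survey can be done online or on paper and is paid per assessment (Section 3.5.5), so a survivor who skips modules may still give a 6-week score. Section 5 also lists retention separately from session completion. This stands too: nothing in the documents shows that those lost would be those who benefited least.

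A reader might infer that the paired analysis overstates the gain by 11-33%. The documents do not support that. The range requires leavers to gain between half (at 80% retention) and none (at 75%) of what completers gain, and the plan says nothing about their gain. Other assumptions give zero, negative or larger values.

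A reader might also infer that moving to the Phase 3B type of model would remove any overstatement. Step 3 shows that it would not when loss depends on the unseen outcome.

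Reporting retention and reasons for drop-out, as planned, will show how many were lost and why. It leaves the outcome estimate unchanged.

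**Conclusion.** The point holds in a limited form. As written, the Phase 2 outcome analysis describes survivors with both scores, while the hypothesis and the analysis text refer to programme participants. At the plan's own thresholds the gap is up to about 8 to 10 of 40, and no Phase 2 text deals with it.

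The direction and size of any bias are unknown. Between the assumptions that leavers gain as much as completers and that they gain nothing, the completer mean exceeds the 40-person mean by 0% to 33%. The bias is negative if leavers gain more, and zero if loss is unrelated to change. These are scenarios built on assumed leaver gains; they are neither estimates nor bounds. The baseline-dependent results further assume a correlation of 0.6 and fairly strong dependence of loss on baseline.

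Priority is low, for the reasons accepted above. The change is still worth making because it costs almost nothing and aligns the analysis with the hypothesis.

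**What to change.** In Section 5, Phase 2, Data Analysis:

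1. Estimate the mean change with a two-time-point mixed model that includes all 40 enrolled survivors, in line with Phase 3B. Enter the baseline and 6-week scores both as responses; a model of the change score, or one with baseline only as a covariate, would again drop survivors with a baseline only. State that this corrects for loss related to the observed baseline score, not for loss related to the unobserved outcome.
2. Add one sensitivity row per outcome that gives zero change to survivors without a 6-week score. With 30 of 40 reassessed and a completer mean of 0.30, that row would read 30/40 × 0.30 = 0.225. It is a scenario, not a lower bound, since leavers could worsen.
3. Label any paired t-test a completer analysis and give its n out of 40.
4. Reconcile the two retention targets (above 75% and above 80%) as they apply to Phase 2.

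The cost is a few sentences, slightly more analysis work and one extra row per outcome, with no new data or visits. The reported gain may be smaller. Section 3.3 refers to Phase 2 as preliminary work already conducted; if its data have been seen, the added analyses should be labelled as specified afterwards.

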## Promoting Follow-Up Care Self-Management for Adolescent and Young Adult (AYA) Childhood Cancer Survivors

[name], MPH

### Phase 3A:

**Data Management:** Usability testing notes will be labeled with an ID number without any identifying data. The Visual Aesthetics of Websites Inventory will only be labeled with an ID number. The key linking subject names and subject numbers will be stored electronically on the PI's password-protected CINJ internal shared drive and destroyed at the end of the study.

**Data Analysis:** The research team will discuss user experience difficulties with the design team for changes during the iterative cycles of usability testing. Given the preliminary work already conducted, we expect 12-20 sessions will achieve data saturation (i.e., no new issues emerge according to pre-specified stopping criteria). Responses to the Visual Aesthetics of Websites Inventory will be summarized with descriptive statistics (e.g., means, frequencies of responses).

### Phase 3B:

**Data Management:** The same procedures used in Phase 2 will be used in Phase 3B, with the exception that TigerConnect (previously called TigerText) will be used for secure messaging as well as secure videoconferencing (instead of doxy.me). Additionally, TigerConnect now allows for secure file transfer so that peer mentors can securely transfer audio recordings to the study team either via Rutgers LiFT or TigerConnect. For participants who consent to be contacted for future studies, the study team will store their contact information separately from research records on the PI's secure One Drive, with access granted only to the PI, study coordinator, and limited authorized research staff. We will store this information for up to 10 years from date of consent.

We will utilize HIPAA compliant Qualtrics survey tool to request the name and contact information of the physician they have seen in the past 12 months to understand their health care utilization during the study period and to obtain their electronic signature on the Release of Medical Record form. Any paper copies will be kept in a locked filing cabinet in the PI's office.

**Data Analysis:** We will examine feasibility through study enrollment rates, retention rates, usability/engagement with online modules and peer mentor, barriers to engagement, and reasons for study drop out. Descriptive analyses (frequencies, means, confidence intervals) will be used to evaluate hypotheses regarding enrollment ( $>50\%$ ), retention ( $>80\%$  complete all surveys), and intervention completion ( $>75\%$  modules/mentor calls). Multilevel modeling (MLM) will be used to examine differences between the intervention and usual care groups over time on transition readiness (RTQ Adolescent Responsibility and TRI total scores). Our primary analysis will consider both time and treatment to be categorical with an interaction between the two. The interaction will be assessed to determine whether change in transition readiness differs between the two groups. The MLM approach assumes any missing observations are missing at random but includes all observed data. Exploratory analyses of additional outcomes (e.g., self-efficacy, adherence to medical appointments and screenings, and health behaviors) will use the identity link or the logit link as appropriate for continuous or binary outcomes.

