#### ***3.1. Duration of Study***

Phase 1: Participants will be asked to complete a one-time interview lasting approximately 60 minutes.

Phase 2: Participants will be asked to complete the intervention over a period of 6 weeks. Participants will be asked to complete 6-week online self-management educational modules and 6 weekly peer mentor calls to facilitate engagement with the online modules and offer specialized support.

Phase 3A: Usability sessions will last approximately 1-hour. Given that usability testing is iterative and design changes are made in response to participant feedback, we will ask some participants if they are willing to review the product another time after changes are made, up to a total of five times. Each session is voluntary and conducted in a way to minimize participant burden.

Phase 3B: Participants assigned to the intervention will be asked to complete it over a period of approximately 8 weeks (which includes 6 peer mentor calls and five corresponding online modules). All participants will be asked to complete surveys at four time points: baseline, immediate post-intervention (~8 weeks after baseline), 3-month follow-up (~5 months after baseline), and 9-month follow-up (~12 months after baseline).

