**Table 1. Feasibility decision rules.**

Feasibility	Unacceptable Rate	Acceptable Rate	Decision rule for claiming Feasibility	Prob. Declare Feasible under Unacceptable Rates	Prob. Declare Feasible under Acceptable Rates
Acceptance	41%	50%	If 50 recruited by the 100th eligible	5%	97%
Retention	70%	80%	40 people complete	5%	94%

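### Phase 3B retention has two different pass criteria, and Table 1's stated chances of declaring feasibility do not follow from its own rules

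*Combined protocol and SAP*

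**What the plan says.** Section 3.3 sets the Phase 3B size: "Total sample size is 50 AYA survivors". It says the size and rules were chosen so that the chance of declaring feasibility would be "approximately 5% under unacceptable rates of acceptance/completion and exceed 95% under acceptable rates". It then repeats the 5% figure for true acceptance and completion of 41% and 70%.

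Table 1 has a column headed "Decision rule for claiming Feasibility":

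| Row | Unacceptable rate | Acceptable rate | Rule | Stated chance of passing (unacceptable / acceptable) |
|---|---|---|---|---|
| Acceptance | 41% | 50% | "If 50 recruited by the 100th eligible" | 5% / 97% |
| Retention | 70% | 80% | "40 people complete" the follow-up (visit not named) | 5% / 94% |

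Section 3.1 lists a post-intervention survey at about 8 weeks and two later visits, both called follow-up: "3-month follow-up (~5 months after baseline), and 9-month follow-up (~12 months after baseline".

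The Phase 3B data analysis text in section 5 evaluates retention descriptively, with confidence intervals, as more than 80% completing every survey ("complete all surveys), and intervention completion"). Hypothesis 1 in section 1.1 also expects retention above 80%, without naming a time point.

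**The concern.** There are two problems.

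**Definition.** Table 1 and section 5 differ in the cutoff (at least 40 versus more than 80%, so at least 41) and possibly in the endpoint (one follow-up visit versus all surveys). Someone who misses the 8-week survey but returns at 12 months could count as retained under Table 1 and not under section 5.

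**Probabilities.** Each pass mark equals the acceptable rate itself: 40/50 = 80% and 50/100 = 50%. When the true rate sits on the pass mark, the chance of reaching it is a little over one half. It cannot be 94% or 97%.

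Section 3.3 states that the sample size rests on the primary feasibility aim, and these two rules are its quantitative basis. If the pass probabilities are far too high, a missed criterion will be read as strong evidence against feasibility when it is weak evidence.

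**Working it through.** **Inputs.** N = 50 (section 3.3). Retention 70% and 80%, rule 40 completers; acceptance 41% and 50%, rule 50 among the first 100 eligible (Table 1). More than 80% of 50 means at least 41 (section 5). Table 1 does not print the retention denominator; I take it to be the 50 enrolled.

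**Formula.** With X ~ Binomial(n, p), the chance of passing is P(X ≥ r) = Σ C(n,k) pᵏ (1−p)ⁿ⁻ᵏ, summed over k = r to n.

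**Attempt to reproduce Table 1.**

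| Rule | At unacceptable rate | At acceptable rate | Stated |
|---|---|---|---|
| Retention, ≥40 of 50 | 7.9% (p = 0.70) | 58.4% (p = 0.80) | 5% / 94% |
| Retention, ≥41 of 50 | 4.0% | 44.4% | 5% / 94% |
| Acceptance, ≥50 of 100 | 4.3% (p = 0.41) | 54.0% (p = 0.50) | 5% / 97% |

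The method of calculation does not explain the gap. For ≥40, the normal approximation gives 6.1% / 50.0% without and 8.2% / 57.0% with continuity correction. No cutoff with n = 50 yields both 5% and 94%.

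**What would give 94% and 97%.** A cutoff of 36 of 50 passes 93.9% of the time at 80%, but 44.7% at 70%. A cutoff of 41 of 100 passes 97.2% of the time at 50%, but 53.8% at 41%. These match the acceptable-rate column and not the printed rules. This may show how the figures arose, but the documents do not say.

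**Chance of missing the retention rule at a true 80%.**
- Table 1 implies 1 − 0.94 = 6%.
- ≥40: 1 − 0.5836 = 41.6%.
- ≥41: 1 − 0.4437 = 55.6% (from unrounded values).

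**True rates at which the rules perform as claimed.**
- Retention, ≥40: 94% is reached at a true rate of 86.7%, and 95% at 87.1%.
- Acceptance, ≥50: 95% is reached at 57.7%, and 97% at 58.8%.

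**How often the two retention criteria disagree.** If both mean the same endpoint, they differ only at X = 40:

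| True retention | 70% | 80% | 85% | 90% |
|---|---|---|---|---|
| P(X = 40) | 3.9% | 14.0% | 8.9% | 1.5% |

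If Table 1 means a single visit, disagreement can be more frequent. The documents do not allow that to be computed.

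**Joint reading.** Section 3.3 could mean that both rules must pass. If the two are independent (my assumption), the chance is 0.0428 × 0.0789 = 0.3% at the unacceptable rates and 0.5398 × 0.5836 = 31.5% at the acceptable ones. This does not recover the stated figures either.

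**Internal check.** Table 1's own 94% already falls short of the more than 95% claimed in section 3.3.

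**The case against.** The best defence is that section 5 sets no decision rule. It describes hypotheses to be evaluated descriptively, and only Table 1 is headed as a rule. An expectation above 80% can sit beside a pass mark of 40, and section 5 may simply supply the detail missing from a short table cell. On a shared endpoint the two differ at one count. That is a fair case for treating the definitional point as a clarification. It does not remove the need for it, because no sentence says that Table 1 governs or that its follow-up means all surveys.

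It is also fair that the unacceptable-rate column is roughly right in places: 4.3% for acceptance, and 4.0% for retention if the cutoff is 41, are close to 5%. The 7.9% for a cutoff of 40 is a modest miss.

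Neither point rescues the 94% or the 97%. Those are the serious errors, and the acceptance gap is the larger of the two. That this is a pilot is a reason not to enlarge it, not a reason to keep wrong probabilities.

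**Conclusion.** The concern holds. Under the printed rules, the chance of passing at the acceptable rates is 58.4% for retention (44.4% with 41) and 54.0% for acceptance, against 94% and 97% stated. The claim in section 3.3 of more than 95% is therefore not met for either criterion. Separately, retention is defined in two ways that conflict at exactly 40 of 50, and the follow-up in Table 1 is not identified.

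This rests on independent participants, 50 as the retention denominator, and the first 100 eligible people as the acceptance denominator. The correction should be made before the feasibility verdict is read, because missing the retention rule says much less about poor retention than Table 1 implies.

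**What to change.** 1. State in sections 3.3 and 5 that Table 1 governs the feasibility verdict, and whether both criteria must be met.
2. Define retention once and use it in section 1.1, Table 1 and section 5. For example: *Retention is completion of [the ~5-month survey / the ~12-month survey / all surveys] among all 50 randomised; feasible if at least 40 (≥80%).* The sponsor chooses the bracketed option and reports the others descriptively. If the sponsor prefers strictly above 80%, the cutoff is 41 throughout. The same choice is needed for enrolment: section 5 says more than 50%, while Table 1 accepts 50 of 100.
3. Restate the Table 1 probabilities: retention 7.9% / 58.4% for at least 40, or 4.0% / 44.4% for at least 41; acceptance 4.3% / 54.0%.
4. Replace the two probability sentences in section 3.3. With the cutoff of 40, for example: *The probability of meeting each criterion is 4.3% (acceptance) and 7.9% (retention) at the unacceptable rates, and 54.0% and 58.4% at the acceptable rates.* The text may add that 95% is reached at about 58% acceptance and 87% retention.

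The cost is text only, with no new data and no change to N. The trade-off is that the present design target can no longer be claimed. Holding error to at most 5% at 70% and passing at least 94% of the time at 80% would need 193 people with a cutoff of 146 (4.9% / 94.3%). Matching the printed figures after rounding would need about 181 with a cutoff of 137 (5.4% / 93.6%). Neither is proposed for a pilot.
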